### 3.4 Independent Variable: One of three injection protocols.

#### Dependent Variables

- Primary Outcome Variable:
  - Visual Analog Scale
  - American Shoulder and Elbow Score
- Secondary Outcome Variable:
  - Single Assessment Numeric Evaluation (SANE)
  - Pittsburgh Sleep Quality Index
  - SF-12

**Functional Outcome:** Visual Analog Scale (VAS) is utilized to measure level or intensity of pain. The scale consists of a horizontal (HVAS) or vertical (VHAS) line, usually 10 cm in length [22] with a descriptor at both ends; the left side reading “no pain at all” and the right side reading “worst pain imaginable.” While this scale is very subjective, patients have an easier time reporting pain on a continuum rather than jumping from categories of none, mild, moderate [23] or severe.

**American Shoulder and Elbow Score (ASES):** is a standardized, 17 item [24], patient self-report tool, which can be completed in about 3 minutes. The patient self-reported section consists of three sections: pain, instability, and activities of daily living. The tool also consists of a physician assessment which includes range of motion, signs, strength, and instability.[25]

**Single Assessment Numeric Evaluation (SANE):** “is an outcome measurement tool used to record the patient’s self-reported function [26]. It is implemented on a scale of 0-100 and correlated with a scale of function from 0-100%. The 100% representing full function (or function prior to injury) and 0% representing no function.”

**Pittsburgh Sleep Quality Index (PSQI):** is a standardized measure for quality of sleep. The tool consists of 24 questions which differentiate “good” and “poor” sleepers and is easy to use for both the patient and the researchers.[27]

**SF-12:** is a standardized general health survey which measures physical and mental health.

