#### *Follow-up Interviews*

Subjects will be contacted by phone to obtain VAS score at day 2, and weeks, 1, 2, and 4 after the injection. They will be instructed to return to clinic at routine follow-up intervals at 6 and 12 weeks after the injection and will again be asked to complete the Outcome Shoulder Questionnaire containing VAS, ASES, SF-12, PSQI scores. Subjects range of motion and shoulder strength will also be collected. All data collected with regards to this study will be kept in a password-protected database, which will only be accessible, by study investigators and the research team.

Study subjects who do not respond to the follow-up phone calls in a timely manner, will be mailed a paper copy of the Follow-up Outcome Shoulder Questionnaire and/or emailed a website link to the same questionnaire on [www.surveymonkey.com](http://www.surveymonkey.com)

	Baseline Shoulder Questionnaire			Follow-up					
	Med Record Review	Pre-Injection	5 Minutes Post Injection	Day 2	Week 1	Week 2	Week 4	Week 6	Week 12
Visual Analog Score (VAS)		X	X	X	X	X	X	X	X
American Shoulder and Elbow Score (ASES)		X						X	X
Single Assessment Numeric Evaluation (SANE)		X	X					X	X

Pittsburgh Sleep Quality Index		X					X	X
SF-12		X					X	X
Range of Motion		X	X				X	X
Dynamometer measurements		X	X				X	X
Pt Characteristics	X							
Injury Characteristics	X							
Co-Morbidities	X							
Pt Hx	X							
Meds	X							
Demographics	X							

4.3 Each phone follow-up should take approximately 10 minutes each and the standard follow-up visits should each take approximately 30 to 45 minutes.

4.4 At each time frame, the subjects will be asked to complete a questionnaire. Blood and tissue samples will not be collected for this study.

4.5 Subjects will be billed for the services received whether they participate in the study or not.

4.6 The only change in clinic practice of shoulder disorders as part of this study protocol will be the randomization of injection medication they will be receiving. Subjects will be prescribed physical therapy as is standard for the treatment of shoulder disorders.

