## **14. Biostatistics**

14.1 Statistical Analysis: The specific purpose of this study is to provide descriptive statistics for both the primary and secondary outcomes. Unpaired t or chi-square tests on all pre-op demographic data. The dependent variables will be analyzed by repeated measure of variance to determine if statistically significant differences exist at follow-up assessment. To protect against Type I error, Tukey tests will be used to ensure the alpha levels ( $p < 0.05$ ) will not be falsely declared significant. This is a prospective double-blinded randomized trial. The investigator of the study and examiner who provides the injection will be blind to which group assignment has been provided. Patients will not be told of the injection type. The billing department will create a study account which will allow billing subjects, for the ketorolac or kenalog, without their knowing which injection they received.

14.2 Sample Size: We are planning a study of a continuous response variable from independent control and experimental subjects with 1 control(s) per experimental subject. In a previous study the response within each subject group was normally distributed with standard deviation 23. If the true difference in the experimental and control means is 12, we will need to study 59 experimental subjects and 59 control subjects to be able to reject the null hypothesis that the population means of the experimental and control groups are equal with probability (power) 0.8 for each diagnostic category of rotator cuff tendinopathy, small to medium rotator cuff tears, and large rotator cuff tear arthropathies. The Type I error probability associated with this test of this null hypothesis is 0.05. To account for a 15% drop out rate we will recruit 66 subjects for each of the 3 arms of the trial in each of the 2 diagnostic categories for a total of 400 patients.

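### Tukey tests alone do not hold Type I error at 5% across two primary outcomes and the diagnostic categories for which the trial is sized

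*Combined protocol and SAP*

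**What the plan says.** Section 14.1 plans one kind of analysis for all outcomes: "The dependent variables will be analyzed by repeated measure of variance to determine if statistically significant differences exist at follow-up assessment". It then gives the only statement on multiplicity: "To protect against Type I error, Tukey tests will be used to ensure the alpha levels", at p < 0.05, are not exceeded by chance findings. It does not say which comparisons form the Tukey family.

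Three other parts of the document bear on this.

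- **Outcomes.** Section 3.4 lists both VAS and ASES under "Primary Outcome Variable". It gives no order between them, no alpha split and no rule that both must succeed.
- **Times.** The follow-up section states "Subjects will be contacted by phone to obtain VAS score at day 2, and weeks, 1, 2, and 4", and the schedule table adds five minutes, week 6 and week 12. That makes seven VAS times after injection. ASES is taken at weeks 6 and 12. No time point is named as primary.
- **Diagnoses.** Section 14.2 sets power 0.8 "for each diagnostic category of rotator cuff tendinopathy, small to medium rotator cuff tears, and large rotator cuff tear arthropathies", and then recruits 66 per arm in each of two categories. On alpha it says: "The Type I error probability associated with this test of this null hypothesis is 0.05". That refers to a single two-group comparison.

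**The concern.** A Tukey procedure holds the error rate for the set of comparisons it is applied to. In a three-arm trial that set is normally the three arm pairs within one analysis of one outcome. It cannot hold the error rate across a second outcome analysed separately, or across a second patient group analysed separately.

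The plan has two primary outcomes of equal standing and sizes each diagnostic category to support its own test. Carried out exactly as written, it leaves several routes to a significant primary result, each at 5%. A report could then cite 14.1 as evidence that the overall error was controlled when it was not. At stake is how much weight one significant primary result can bear, for example on ASES alone in one category.

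**Working it through.** **1. The plan's own figure.** Inputs from 14.2: difference 12, SD 23, two-sided alpha 0.05 (sidedness is not stated; the null is equality), power 0.8. With 59 per group the noncentrality is (12/23) × √(59/2) = 2.834 on 116 df. The critical t is 1.981, so power is about Φ(2.834 − 1.981) = Φ(0.853) ≈ 0.80 (exact noncentral t: 0.802). The stated 59 is reproduced. It is the size for one unadjusted two-group comparison in one category on one outcome, which 14.2 does not name.

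**2. What Tukey does within one family.** For three arms of 59 the Tukey critical t is 2.364, a pairwise alpha of about 0.019. This holds the three pairs jointly at 5%. The sized comparison then has power of about Φ(2.834 − 2.364) = Φ(0.47) ≈ 0.68, not 0.80.

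**3. Simple bounds across families.** If k families at 5% were independent, the chance of at least one false positive would be 1 − 0.95^k:

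- k = 2 (two outcomes, diagnoses pooled; or one outcome in two categories): 9.75%
- k = 4 (two outcomes, two categories): 18.5%
- k = 18 (nine outcome-times, two categories): 60.3%

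Patients in different categories are independent, but outcomes and visits within a patient are correlated. The correlated figures are therefore lower.

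**4. Simulation with correlation.** The setting is no true effect, three arms of 59, Tukey at 5% in each family, and seven VAS and two ASES measurements with a common correlation ρ. There were 8,000 runs per setting for most entries. The documents give no correlations, so ρ = 0.3 to 0.9 is an assumption. Two categories are combined as 1 − (1 − p)². The error rate hardly depends on sample size, so the one-category figure also serves for a pooled analysis.

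| Family at 5% | Diagnoses | ρ = 0.3 | 0.5 | 0.7 | 0.9 |
|---|---|---|---|---|---|
| One arm-effect family per outcome | pooled | 9% | 8% | 8% | 6% |
| | two categories | 17% | 14% | 15% | 12% |
| One visit per outcome | pooled | 10% | 9% | 9% | 7% |
| | two categories | 18% | 18% | 17% | 14% |
| Every outcome at every visit (9) | pooled | 34% | 27% | 21% | 13% |
| | two categories | 56% | 47% | 38% | 25% |

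Letting the correlation between VAS and ASES differ from that between visits (0.7 between visits, 0.3 between outcomes) gives the highest arm-effect figures: 10.0% pooled and 19.0% over two categories. If visit-by-visit tests are run only after a significant main effect or interaction, the figure over two categories is about 18–25%.

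**The case against.** The strongest reply is that 14.1 plans a repeated-measures analysis of each outcome, not a separate test at every visit. The Tukey family is undefined and could be the arm effect, or all arm-by-time cells. Either would deal with time within one outcome. This stands. A reader might infer from the schedule that the error rate is 38–56%, but that needs nine ungated Tukey analyses per category, which the plan does not describe. It also needs correlations no higher than 0.7; at 0.9 the same reading gives about 25%.

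Second, 14.1 does not say that diagnoses are analysed separately, and Hypothesis 1 in section 1.2 is a single hypothesis over a variety of pathologies. This also stands. Separate testing is an inference from the sizing in 14.2, and on a pooled analysis the error is at most about double 5%. Statisticians also differ on whether distinct patient groups must share one error rate. The two-outcome problem remains on either view.

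Third, 14.1 calls the purpose descriptive, and the documents define no rule for declaring the trial a success. A reader might infer that the plan licenses a claim of success on any one comparison, but it does not say so. Even so, the same paragraph plans significance tests and section 1.2 states a superiority hypothesis, so the error rate matters.

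**Conclusion.** The concern holds. Tukey tests, the only protection named, do not adjust across VAS and ASES or across diagnostic categories, so the assurance in 14.1 does not hold for the primary outcomes as a set. On readings that respect the repeated-measures analysis, the false-positive chance is about 6–10% with diagnoses pooled and about 12–19% with two categories tested separately. The range 25–56% is a worst case and should be quoted only as such.

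These figures rest on assumed correlations of 0.3 to 0.9, on two categories, and on separate testing where stated. The category count is itself unsettled: 14.2 names three and recruits two, and section 3.5 mentions both two and five. The direction does not depend on these assumptions. Any two families at 5% that do not always agree exceed 5% together. It would go too far to say that Tukey is the wrong tool, or that the plan's error rate is known to be many times 5%. The documents fix neither the family nor the correlations.

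**What to change.** In 14.1:

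- Name one primary outcome, one time point (for example week 12, when both scores are collected) and one arm contrast.
- Choose the contrast to agree with both the stated aim and the sizing, and reconcile those passages. Sections 1.1 and 3.1 compare ketorolac with corticosteroid. Section 14.2 sizes experimental against control, and the study-group lists give the control label to the Marcaine-only arm. Section 14.2 should also say which outcome its SD of 23 and difference of 12 refer to.
- State whether the primary test is pooled over diagnoses, adjusted for diagnosis, or run per category. Two categories at 0.05 each would still give 1 − 0.95² = 9.75%. If per category, split alpha (for example 0.025 each) or test the categories in a fixed order.
- Test the second primary outcome at the same visit only if the first is significant.
- Label all other outcomes, times and arm pairs secondary and report them with confidence intervals.
- Limit the Tukey statement to pairwise arm comparisons within one analysis.

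In 14.2, restate the power to match. At alpha 0.025 the critical t is about 2.27, so 59 per group gives about Φ(2.834 − 2.27) = Φ(0.56) ≈ 0.71; about 72 per group would restore 0.80. A pooled test with 2 × 59 = 118 per arm and the same difference and SD has noncentrality (12/23) × √(118/2) = 4.01 and power of about 0.98.

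The cost is mostly wording, with no new visits or data. Fewer results can be called confirmatory, power falls if alpha is split, and settling the contrast may reopen the sample-size justification.

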### **3. Concise Summary of Project**

**3.1 Study Design:** The proposed study is a three arm, double-blinded, prospective randomized controlled clinical trial with follow-up immediately after the injection and at day 2, and weeks 1, 2, 4, 6, and 12. In this study we will compare the effectiveness of ketorolac compared to corticosteroid.

Ketorolac is an injectable solution which should be stored at 15 C to 30 C (59 F to 86 F) and protected from light. Marcaine (Bupivacaine) should be stored at room temperature, between 20 C to 25 C (68 F to 77 F). And Kenalog (triamcinolone) should be stored at controlled room temperature, 20°–25°C (68°–77°F), avoid freezing and protect from light. Do not refrigerate.[18]

Medications are stored in a locked cabinet at room temperature. The Research Team will prepare the appropriate injection medication according to group assignment at the time of the appointment. Injections will not be prepared beforehand. Injections will be prepared by inserting the syringe into both bottles and drawing the required amount. The syringe contents will be masked from the physician.

**Study Groups:** Subjects being seen for a rotator cuff injury will be randomized into one of three treatment groups pertaining to their pathology. The intervention will begin once the subject has consented and answered the Baseline Outcome Shoulder Questionnaire. The Baseline Outcome Questionnaire consists of the Visual Analog Score, American Shoulder and Elbow Score, Single Assessment Numeric Evaluation, Pittsburgh Sleep Quality Index, SF-12, range of motion and measure the subjects shoulder strength by using a

dynamometer, and questions pertaining to patient characteristics, injury characteristics, co-morbidities, patient history, medications, and demographics.

A dynamometer is a small, hand-held device which the subject presses against. By pressing against the device, it measures the strength of their shoulder.

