Randomization: Subjects will be recruited from the UT Southwestern Orthopaedic Surgery Clinic and John Hopkins clinics: Johns Hopkins Orthopaedics, Johns Hopkins Community Physicians, and Southern Maryland Orthopaedic and Sports Medicine Division of Centers for Advanced Orthopaedics, from patients who meet the inclusion criteria. As this study design will be prospective randomized double-blinded, we will utilize computer generated block randomization technique. After identifying a patient who meets the inclusion criteria by history, physical examination, and obtaining informed consent, HIPPA, health screen, and baseline measurements, subjects will be randomized into one of three cohorts: 1) Control (Marcaine injection), 2) NSAID injection (ketorolac & Marcaine injection), or 3) Steroid injection (kenalog & Marcaine injection). To ensure that the number of subjects is about the same in the three arms of the study, the randomization scheme will assign patients in a 1:1:1 ratio in randomly permuted blocks of assignments stratified by clinical center. Block size will be determined randomly and the patient will be the unit of randomization.

Enrollment and randomization results will be documented in the patient's chart according to protocol. The randomization allocation will be blinded to both the patient (initially) as well as the physician performing the injection and the investigator conducting statistical analysis of the results. Given the nature of this study looking at the effects of this intervention on multiple shoulder pathologies we anticipate approximately 200 subjects per diagnostic category would be needed for enrollment and complete follow-up.

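### Power is claimed within each diagnostic category, but allocation is stratified by center only and nothing enforces the stated category targets

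*Combined protocol and SAP*

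**What the plan says.** The sample size is built category by category. Section 14.2 asks for 59 patients per group "with probability (power) 0.8 for each diagnostic category of rotator cuff tendinopathy, small to medium rotator cuff tears, and large rotator cuff tear arthropathies", and then adds an allowance for dropout: "we will recruit 66 subjects for each of the 3 arms of the trial in each of the 2 diagnostic categories". That makes 400 in all. Section 3.5 repeats about 66 per arm in both diagnostic groups. The Randomization paragraph of Section 14 adds that "we anticipate approximately 200 subjects per diagnostic category would be needed for enrollment and complete follow-up".

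The allocation rule is in that same paragraph: "the randomization scheme will assign patients in a 1:1:1 ratio in randomly permuted blocks of assignments stratified by clinical center". Block size is random. Center is the only stratification factor named.

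Section 3.1 (Study Groups) says that subjects "will be randomized into one of three treatment groups pertaining to their pathology". It then lists three groups under full-thickness tear and three under tendinitis. The three injections are the same under both headings, and no separate allocation list is described.

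No section closes a category once it reaches its number. Section 11 has the DSMB review recruitment overall, not by diagnosis.

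**The concern.** Power is claimed inside each category, while allocation is controlled inside each center and enrolment only through the total. A site that follows Section 14 literally takes the next assignment from one center list, whether the patient has tendinitis or a tear. Two things are then left open.

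- **Arm sizes within a category.** The 1:1:1 ratio holds for the center as a whole. Within a diagnosis the arms vary by chance.
- **Size of each category.** A target of about 200 is written down, but nothing stops the commoner diagnosis from using up places meant for the other. If the mix is uneven, the smaller category ends below 66 per arm, and no later analysis can restore the missing patients.

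**Working it through.** **Inputs from Section 14.2.** The difference is 12 ("If the true difference in the experimental and control means is 12"), the SD is 23, power is 0.80 and dropout is 15%. On alpha: "The Type I error probability associated with this test of this null hypothesis is 0.05". Sidedness is not stated. I take it as two-sided, because the aim is to "reject the null hypothesis that the population means of the experimental and control groups are equal" and because only the two-sided test reproduces the plan's figure (one-sided gives 46).

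**Step 1: the plan's own figure.** n per arm = 2 × SD² × (1.960 + 0.842)² / difference² = 2 × 529 × 7.85 / 144 = 57.7, so 58. The t-based solution is 58.64, so 59, as stated. Power at 59 per arm is 0.802 (t).

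**Step 2: the planned category.** 66 × 3 = 198 per category, and 198 × 2 = 396, or about 400. After dropout, 66 × 0.85 = 56.1 per arm remain, with power 0.78. This is the baseline for what follows. (66 is short of 59 / 0.85 = 69.4, so 70. That is a separate matter and is not counted here.)

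**Step 3: no stratum for diagnosis, even split.** Take 396 patients, 132 per arm, 198 per category, with balance controlled only overall. The variance of one arm's size within a category is 198 × (1/3) × (2/3) × (198/395) = 22.06, so the SD is 4.7. Three arms sum to a fixed total, so the difference between two arms has variance 3 × 22.06 = 66.2, SD 8.1. As a share of 132, the diagnostic mix of two arms differs with an SD of about 6 percentage points.

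A simulation (4,000 runs per setting) with 2 or 4 equal centers and random blocks of 3, 6 or 9 gives the table below. The number of centers and the block sizes are assumptions, because the documents do not state them. Power here uses the normal approximation with 15% dropout.

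| Within one category of 198 | Center only | Center and diagnosis |
|---|---|---|
| SD of an arm's size | about 4.7 | 0.8 to 1.1 |
| Largest minus smallest arm, median | 9 | 2 |
| Same, 95th percentile | 19 | 3 to 4 |
| Chance that some arm starts below 59 | 16 to 17% | 0% |
| Mean power, one pair of arms | 0.787 | 0.789 |
| 2.5th percentile of that power | 0.757 | 0.783 to 0.786 |

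Across both categories together, at least one of the six cells starts below 59 in about 24 to 25% of runs.

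**Step 4: uncontrolled case mix.** With 400 enrolled and a smaller category holding a share s, the evaluable number per arm is m = 400 × s / 3 × 0.85. Power is from the noncentral t with noncentrality (12/23) × √(m/2). The splits are assumed.

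| Split | Smaller category, per arm | Evaluable per arm | Power, smaller | Power, larger |
|---|---|---|---|---|
| 50:50 | 66.7 | 56.7 | 0.786 | 0.786 |
| 60:40 | 53.3 | 45.3 | 0.690 | 0.856 |
| 70:30 | 40.0 | 34.0 | 0.564 | 0.904 |
| 80:20 | 26.7 | 22.7 | 0.404 | 0.937 |

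The 50:50 row is slightly above the 0.78 of Step 2 because it uses 400 rather than 396 patients.

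**Step 5: what counts as a category.** Section 14.2 names three categories for power but multiplies by two for the total. Section 3.5 mentions two and then five. Section 6 admits three diagnoses, including tear arthropathy. Section 3.1 lists injection groups for only two. If three categories shared 400 equally, each would have 400 / 9 = 44.4 per arm, 37.8 evaluable, and power 0.61.

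**The case against.** The plan does state category numbers: 66 per arm in each of two categories, about 200 each. A site that simply filled 400 places with whoever came to clinic would depart from Section 14.2. This stands. It would be wrong to say that the trial has no category targets; what is missing is a rule that enforces them.

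Section 3.1 may mean randomization within pathology, with Section 14 describing the strata incompletely. This stands in part. The phrase is ambiguous, and identical injections under both headings do not settle it. Section 14 is the only place that states how assignments are generated, and it omits diagnosis. Either way the two sections need one consistent statement.

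The missing stratum does little harm to power. This stands. A reader might take the 24 to 25% of runs with a cell below 59 as a sign of serious loss, but mean power moves only from 0.787 to 0.789. A perfectly balanced 66 falls to 56 after dropout anyway. A reader might also infer that unequal diagnostic mix biases a pooled comparison. It does not: assignment is still random, so the imbalance is chance, and a model that includes diagnosis can adjust for it.

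Hypothesis 1 covers shoulder pathologies together, and Section 14.1 sets out no analysis by category. This is true and limits how far one can say that each category is promised its own answer. The sample size, however, rests entirely on comparisons within a category.

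**Conclusion.** The mismatch is real and cheap to repair. Its two parts differ in weight.

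Leaving diagnosis out of the strata costs balance and a little precision: a median arm gap of 9 instead of 2 at an even split, with power for a pair of arms rarely below about 0.76. The uncontrolled mix is the larger exposure, with power in the smaller category of about 0.69 at 60:40 and 0.56 at 70:30, against 0.78 as planned.

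Those lower figures show sensitivity, not a demonstrated shortfall. The documents give no expected case mix, so a reader should not conclude that either category will be underpowered for this reason. The figures also rest on a two-sided test, two categories, and dropout equal in all arms.

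**What to change.** In the Randomization paragraph of Section 14, name clinical center and diagnostic category as stratification factors, with the category recorded from the clinic diagnosis before randomization. Add that enrolment to a category closes when it reaches its planned number, about 198 to 200. Amend Section 3.1 to describe the same scheme.

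This needs one list of categories. Reconcile Sections 3.1, 3.5, 6 and 14.2 so that every eligible patient, including one with tear arthropathy or a partial-thickness tear, falls in exactly one stratum.

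The cost is a revised computer-generated list and a short amendment. With two categories the number of strata doubles, which leaves more incomplete blocks. The commoner diagnosis may close early while the other fills, which could lengthen recruitment.
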